10.2.10 Urgent Safety Measures

In accordance with the principles of Good Clinical Practice (GCP), the Investigator(s) has/have primary responsibility for assuring patient safety throughout the performance of study procedures. An urgent safety measure is defined as any measure which an Investigator may need to implement which is a deviation from, or a change in, the protocol to eliminate an immediate hazard(s) to trial patients without prior IEC/IRB approval/favorable opinion.

The Investigator may take appropriate urgent safety measures in order to protect the patients of a clinical trial against any immediate hazards to their health or safety. However, the Investigator must inform the Sponsor/CRO within 24 hours of having taken such measures.

The Sponsor in turn shall immediately, and in any event no later than 3 days from the date the measures are taken, give written notice to the licensing authority and the relevant IEC/IRB of the measures taken and the circumstances giving rise to those measures.

All urgent safety measures must be reported to the Sponsor/CRO by using the SAE contact numbers listed in Section 10.2.9 within 24 hours of having to take such a measure(s). Such reports can be initiated by telephone but must be officially documented by the Investigator (by email or fax) and must include details of what measures were taken and the circumstances giving rise to those measures.

10.2.11 Pregnancy Reporting

This process is aimed at ensuring the appropriate monitoring of the potential risk related to IMP exposure of pregnant women and/or fetuses as well as the risks associated with exposure of a father, regarding congenital abnormalities or birth defects in their offspring. It also ensures compliance with applicable international and local regulations.

The requirements are applicable to all patients following exposure to IMP.

Female trial patients: The trial patient must be advised by the Investigator to inform him/her immediately if she suspects she may be pregnant and believes that conception occurred within 30 days after administration of IMP.

Male trial patients: The trial patient must be advised by the Investigator to inform him/her immediately if they suspect their partner became pregnant within 30 days after the patient received an administration of IMP.

When a trial patient reports a pregnancy (post-IMP administration) to the Investigator, a pregnancy test should be arranged for the trial patient (or their partner) by the Investigator within 7 days of the pregnancy being reported.

The Investigator must inform the Sponsor/CRO within 24 hours of receiving positive pregnancy test results by using a copy of the relevant eCRF page (demography or AE) or via email. The Investigator should include an estimated date of conception when communicating with the Sponsor/CRO.

10.3 Other Variables

10.3.1 Demographic Data

Subject demographic data date of birth, race, gender, weight and height will be recorded at screening. Subject age at the time of randomization will be calculated from the date of birth and the date of baseline. BMI will be calculated from height and weight. If local regulations do not permit collection of specific demographic items e.g. date of birth, a dummy date will be used in accordance with local practice.

10.3.2 Medical and Surgical History

The subjects' relevant medical and surgical history will be recorded at Screening and Baseline.

10.3.3 Prior and Concomitant Medication and Procedures

Prior and concomitant medications and procedures will be recorded between Screening and Follow-up 3.

10.4 Appropriateness of Measurements

All assessments and measurements are appropriate and generally regarded as standard medical practice.

11 DATA HANDLING AND QUALITY ASSURANCE

11.1 Completing and Signing Case Report Forms

For eCRFs, data will be entered by trained site personnel with reasons given for any missing data. Any errors should be corrected within the electronic system. The audit trail will record all changes made, the date and time of the correction, and the person correcting the error and the reason for the correction. The appropriate electronic signature will be provided.

Any data recorded directly in the eCRF, for which no other written or electronic record will be maintained in the patient's medical record, will be considered source data and should be signed by the Investigator(s) (e.g., results of physical examinations, vital signs testing, or the Visipaque™ or saline placebo administration procedure).

11.2 Clinical Data Management

The Contract Research Organization (CRO) will be responsible for the processing and quality control of the data. Data management will be carried out by the CRO. The handling of data, including data quality control, will comply with all applicable regulatory guidelines.

11.3 Archiving

All study documentation at the Investigator site and Sponsor site will be archived in accordance with International Conference on Harmonisation (ICH) E6-GCP and the Sponsor/CRO's quality standards and standard operating procedures (SOPs).

All study documentation at the Investigator site and Sponsor site will be archived for a minimum of 15 years following completion or discontinuation of the study, unless notified otherwise by the Sponsor or a longer period is required by local legislation. The Principal Investigator is responsible for informing the Sponsor should he/she no longer be responsible for the study documentation and must provide details of the new responsible person. The Principal Investigator must request written agreement from the Sponsor before destruction of archived study documentation.

12 STATISTICAL METHODS AND PLANNED ANALYSIS

The data will be analyzed by the Sponsor and/or designated CRO. Any data analysis carried out independently by the Investigator should be submitted to the Sponsor before publication or presentation.

Data from participating centers in this protocol will be combined so that an adequate number of patients will be available for analysis. The data will be summarized with respect to demographic and baseline characteristics, efficacy observations and measurements, and safety observations and measurements.

12.1 General Statistical Considerations

Tabulations of summary statistics, graphical presentations, and statistical analyses will be performed with SAS® software, Version 9.2 or higher. Descriptive statistics for continuous data in summary tables will include the number of patients in the analysis (n), mean, standard deviation, median, and range (minimum, maximum). Descriptive statistics for categorical data in summary tables will include counts and percentages. The last observation prior to administration of Visipaque™ or saline placebo will be used as the baseline value for calculating changes from baseline after administration of Visipaque™ or saline placebo. All data obtained on the eCRF and entered into the database will be provided in separate data listings showing individual patient values. All summary tables and data listings will be separated by treatment groups. Statistical tests will use a 0.05 significance level for 2-sided tests and 0.025 for 1-sided tests. The planning and reporting of statistical analysis will be carried out as described in the Sponsor/CRO's SOPs governing clinical studies.

12.2 Definitions

CKD staging [National Kidney Foundation 2002] [Kirsztajn 2009]:

Stage I: kidney damage with normal or high GFR (≥ 90 mL/min/1.73 m²)

Stage II: kidney damage with mildly decreased GFR (60-89 mL/min/1.73 m²)

Stage IIIA: moderately reduced kidney function (GFR 45-59 mL/min/1.73 m²)

Stage IIIB: moderately reduced kidney function (GFR 30-44 mL/min/1.73 m²)

Stage IV: severely reduced kidney function (GFR 15-29 mL/min/1.73 m²)

Stage V: very severe or end-stage kidney failure (GFR <15 mL/min/1.73 m²)

AKIN Serum Creatinine Criteria for AKI [AKIN 2015] [Mehta et al. 2007]:

Stage 1: a SCr increase of ≥ 0.3 mg/dL (≥ 26.4 µmol/L) or increase to $\geq 150\%$ to 200% (≥ 1.5 - to 2.0-fold) from baseline within 48 hours

Stage 2: a SCr increase to >200% to 300% (>2.0- to 3-fold) from baseline within 48 hours

Stage 3: a SCr increase to >300% (>3.0-fold) from baseline or SCr \geq 4.0 mg/dL (\geq 354 μ mol/L) with an acute increase of \geq 0.5 mg/dL (\geq 44 μ mol/L) within 48 hours

Standard definition of CIN [[Mehran and Nikolsky 2006](#)]:

Increase in SCr of 0.5 mg/dL or more in the 24 to 72 hours after the CT scan.

Waikar's definitions of AKI [[Waikar and Bonventre 2009](#)]:

Stage 1: 0.3 mg/dL increase in SCr over 24 hours or a 0.5 mg/dL increase in SCr over 48 hours

Stage 2: 0.5 mg/dL increase in SCr over 24 hours or a 1.0 mg/dL increase in SCr over 48 hours

Stage 3: 1.0 mg/dL increase in SCr over 24 hours or a 1.5 mg/dL increase in SCr over 48 hours.

12.3 Populations for Analysis

12.3.1 Determination of Safety Population

The safety population will include all patients who are randomized to receive VisipaqueTM or saline placebo and have post-randomization observations. This population will be based on the study treatment the patient is randomized to. Mortality and morbidity, image quality, and other safety outcome measures will be evaluated in the safety population.

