9.2 Baseline Visit

The Baseline visit will take place within 14 days of the Screening visit.

At the Baseline Visit, the following will be collected and/or performed:

Before administration of Visipaque™ 320 mgI/mL or saline placebo the following will be collected and/or performed:

- All female patients of child-bearing potential will undergo a urine pregnancy test.
- Inclusion/exclusion criteria will be checked.
- General medical/surgical history.
- Prior and concomitant medication.
- Physical examination.
- Vital signs (blood pressure, heart rate, respiration rate) in the sitting position.
- The patient will be randomized to the CECT arm or NECT arm by IWRS/IVRS.
- Blood samples will be drawn for laboratory evaluation (local clinical chemistry and hematology if not already done at screening and for central determination of SCr, cystatin C and N-GAL); see [Table 2](#).
- Urine sample for clinical chemistry (if not already done at screening), and Nephrocheck® biomarkers (where local NephroCheck® testing is available).
- The patient will receive oral hydration (500 mL of fluids) following collection of blood samples for central analysis of SCr. In case of concern about the patient's compliance and/or capability to follow the oral hydration instructions, i.v. administration of isotonic crystalloid solution (saline or bicarbonate) may be considered. Decision on use of i.v. hydration will be made and documented before randomization (to be implemented regardless of whether the subject is randomized to the NECT or CECT arm).
- Pre-treatment AEs, SAEs and critical events, including EVAR-related post-baseline events (from time of signing informed consent).

- Optional ORFM; for a subset of patients at selected sites, MB-102 will be administered 1 hour prior to Visipaque™ or saline placebo.

Administration of Visipaque™ 320 mgI/mL or saline placebo:

- Patients in the CECT arm will receive 100 mL of Visipaque™ Injection 320 mg I/mL followed by a 10 mL saline flush.
- Patients in the NECT arm will receive 100 mL of saline placebo, followed by a 10 mL saline flush.
- Study personnel must remain vigilant for the occurrence of AEs, particularly those that may be life-threatening. Personnel who are trained in the acute management of anaphylaxis and other emergencies and who have access to appropriate clinical supplies must be immediately available for 30 minutes after dosing.

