12.3.3 Determination of Per-Protocol Set

The per-protocol (PP) set will include all patients who receive VisipaqueTM or saline placebo, have both baseline and post-scan SCr measurements, and do not have any major protocol deviations with the potential of impacting data analyses and/or interpretability. This population will be based upon the treatment that the patient is randomized to. Patients in the saline placebo group who receive contrast medium prior to the 48 hour assessments (Follow-up 1) will be excluded from the analysis. Patients in the VisipaqueTM group who receive additional doses of contrast medium prior to the 48 hour assessments (Follow-up 1) will also be excluded from the analysis. Primary, secondary and exploratory analyses will be repeated using the PP set.

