12.7.2 Exploratory Analyses

12.7.3 Other Safety Variables and Analyses

Other safety variables will be analyzed for the Safety Population.

In addition to the Investigator's evaluation of normal or abnormal, the Sponsor will internally evaluate clinical laboratory, vital-sign, and ECG results for an outlying result or extreme value as follows:

- An outlying result for any numeric laboratory result, vital-sign result, or ECG interval measurement will be any post-administration change from baseline that meets either of the following criteria:
 $<25\text{th Percentile} - 1.5 * (\text{interquartile range})$ OR
 $>75\text{th Percentile} + 1.5 * (\text{interquartile range})$.
- An extreme value for any numeric laboratory result, vital-sign result, or ECG interval measurement will be any post-administration change from baseline that meets either of the following criteria:
 $<25\text{th Percentile} - 3 * (\text{interquartile range})$ OR
 $>75\text{th Percentile} + 3 * (\text{interquartile range})$.

Post-administration changes from baseline will be summarized by mean, SD, minimum, and maximum at each time point for each treatment group (CECT vs NECT). Plots and shift tables of all post-administration changes from baseline vs time will be generated and examined for trends and relatively large individual changes from baseline.

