12.7.3.4 Adverse Events

AEs and SAEs will be coded using MedDRA and all reported events will be listed for the safety population. Treatment-emergent AEs are defined as AEs that occur from the time of treatment administration through Follow-Up 3. The number and percentage of patients with 1 or more AEs will be summarized by system organ class and preferred term overall and by treatment group (CECT vs NECT). Summaries will also be presented by AE intensity and judged relationship to Visipaque™ or saline placebo. Treatment-emergent SAEs are defined as SAEs that occur from the time of treatment administration through Follow-Up 3. Treatment-emergent SAEs will be presented by treatment group for the safety population.

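### Adverse events are tabulated by randomized arm in a safety set that does not require dosing; the dilution is probably small, and a dosed set grouped by the agent injected at Baseline would remove it cheaply

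*Combined protocol and SAP*

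**What the plan says.** Section 12.3.1 (Determination of Safety Population) admits patients who are randomized "and have post-randomization observations". Receipt of Visipaque or saline is not a condition. On grouping it says: "This population will be based on the study treatment the patient is randomized to". On use it says: "Mortality and morbidity, image quality, and other safety outcome measures will be evaluated in the safety population".

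Section 12.7.3 repeats the use: "Other safety variables will be analyzed for the Safety Population". Section 12.7.3.4 says: "AEs and SAEs will be coded using MedDRA and all reported events will be listed for the safety population", and sets the counting window: "Treatment-emergent AEs are defined as AEs that occur from the time of treatment administration through Follow-Up 3".

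The other two analysis sets differ. The full analysis set (12.3.2) and the per-protocol set (12.3.3) both require that the patient received Visipaque or saline. The per-protocol rule also foresees "Patients in the saline placebo group who receive contrast medium prior to the 48 hour assessments" and removes them, but that set serves the primary, secondary and exploratory analyses, not the AE tables.

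Section 9.2 lists randomization ("The patient will be randomized to the CECT arm or NECT arm by IWRS/IVRS") before blood sampling, hydration and injection, so a patient can be randomized and not dosed.

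The plan is not uniform on this. Section 12.9 speaks of data from all patients dosed, while 12.10 speaks of all randomized patients with post-randomization observations. Section 12.10 lets the SAP specify otherwise, but no separate SAP text on this point is in the document supplied, and it contains no as-treated safety summary.

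**The concern.** A table of adverse events is read as a statement about what was injected. Under the stated rule two kinds of patient blur it.

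- **Wrong agent at Baseline.** If a patient randomized to saline is injected with contrast, the events that follow appear in the saline column. Sections 10.2.6 and 12.7.3.4 judge relationship by agent, so an event judged related to Visipaque could sit under saline.
- **No injection.** A patient randomized but not dosed, with some later observation, counts in the denominator but cannot have a treatment-emergent event, because the window opens at administration.

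The primary objective in section 5 is to demonstrate the safety of contrast. A definition that pulls the two columns together leans towards that conclusion, even if only slightly, and a reader of the clinical study report could not see by how much.

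**Working it through.** **1. The plan's own figures.** The documents give no crossover share and no undosed share, so there is no figure on this point to reproduce. The 582 patients per group (12.8) is used below only for scale. It does reproduce. With 10% in both arms, a 5-point margin and one-sided 0.025, the score formula uses restricted rates of 13.03% and 8.03%, so v0 = 0.1303×0.8697 + 0.0803×0.9197 = 0.1871, and v1 = 2×0.10×0.90 = 0.18. Then n = [(1.960×√0.1871 + 0.842×√0.18)/0.05]² ≈ 581 per group, and power at 582 is 80.1%.

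**2. Dilution formula.** Let pc and ps be the treatment-emergent AE rates after contrast and after saline. Let c be the share of the saline arm injected with contrast, and u the undosed share, taken as equal in both arms. Undosed patients contribute no treatment-emergent event.

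- Contrast column: (1−u)·pc
- Saline column: (1−u−c)·ps + c·pc
- Difference: (1−u−c)·(pc−ps)

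The tabulated difference is therefore the true difference times (1−u−c), whatever the two rates are.

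**3. Numbers.** Assumed rates are pc = 15% and ps = 10%, a true difference of 5.00 points. All values of c and u are assumptions.

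| c | u | Contrast column | Saline column | Difference (points) | Factor |
|---|---|---|---|---|---|
| 1% | 0% | 15.00% | 10.05% | 4.95 | 0.99 |
| 2% | 2% | 14.70% | 9.90% | 4.80 | 0.96 |
| 5% | 2% | 14.70% | 10.05% | 4.65 | 0.93 |
| 10% | 5% | 14.25% | 10.00% | 4.25 | 0.85 |

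The first three rows span the range treated as plausible: 1-7% relative dilution, or 0.05-0.35 points. The last row is an outer case.

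**4. Scale.** The standard error of a 15% versus 10% difference with 582 per group is √[(0.15×0.85 + 0.10×0.90)/582] = √(0.2175/582) = 1.93 points. A shift of 0.05-0.35 points is well inside sampling noise.

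**5. Direction of the undosed part.** This rests on similar undosed shares. If 2% are undosed in the contrast arm only, the difference is 14.70 − 10.00 = 4.70. If 2% are undosed in the saline arm only, it is 15.00 − 9.80 = 5.20, so the difference grows. With equal shares and no crossover the ratio of rates is unchanged: 14.70/9.80 = 1.50.

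**6. Rare serious reactions.** Crossover of 1-5% of 582 is about 6-29 patients. At the 1-2 per 10,000 quoted in 6.3 (given there for low-osmolar media, while the study agent is iso-osmolar), the expected number of serious acute reactions among them is 6×0.0001 = 0.0006 to 29×0.0002 = 0.006.

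**The case against.** The strongest reply is that little is at stake, and much of it stands.

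- Randomization and injection fall at the same Baseline Visit (9.2), and dosing is supervised (8.7). Undosed patients who still have later observations, and wrong injections, should be few.
- The AE tables are descriptive and carry no hypothesis test.
- Laboratory and vital-sign summaries use post-administration values and changes (12.7.3 to 12.7.3.2). An undosed patient has nothing to contribute there, so for those summaries only the wrong-agent route applies.
- Section 12.7.3.4 also describes a table of patients with one or more AEs without expressly limiting it to treatment-emergent events, and AEs are collected from consent. The undosed patient's inability to add an event holds only for treatment-emergent counts.
- The study is unblinded (8.4), the vial code and volume are recorded (8.7), causality is assessed for each AE, and individual listings are provided (12.1). A misplaced reaction can be found. It would still be counted in the wrong column, which is the part of the concern that remains.

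A further objection concerns remedies. Moving every saline patient who receives contrast before Follow-up 1 into the contrast group would regroup on a post-randomization event. A patient given contrast later because of a complication would bring along events that preceded or prompted it. That objection is right, and it shapes the fix below.

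Two stronger readings are tempting. First, a reader might infer that the 6-month noninferiority tests are compromised. With a true difference on the 5-point margin, the rates above and 582 per group, the false-noninferiority rate moves from 2.5% to 3.8% at c = 5%, u = 2%. But that calculation gives undosed patients no events, although they can die or be hospitalized, and it assumes event rates of 10-15% that the documents do not state for those outcomes. As-randomized grouping is defensible there. Second, a reader might infer that a serious contrast reaction is likely to be hidden under saline. The expected count of at most 0.006 does not support that.

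**Conclusion.** The point holds as a matter of stated definition: the set used for AE and SAE summaries is the only one of the three with no exposure requirement, and it is grouped by allocation and not by injection. The consequence is probably small: about 1-7% relative dilution under assumed crossover of 1-5% and undosed shares of 0-2%, with the undosed share similar in the two arms. Wrong-agent injections in the saline arm pull the columns together. The undosed contribution does so only if it is not concentrated in the saline arm.

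The documents do not support extending this to the primary result. The safety-population definition does not govern the AKI test, which uses the full analysis set, requires dosing, and is repeated in a per-protocol set that removes saline patients given contrast before Follow-up 1. This is a cheap improvement, not a threat to the trial's conclusion.

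**What to change.** In 12.3.1, add a set for the AE, SAE, laboratory and vital-sign summaries: all patients who received a study injection, grouped by the agent actually injected at Baseline. Refer to it in 12.7.3 and its subsections, and align 12.9 and 12.10 with it.

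For contrast given after the Baseline injection and before Follow-up 1, leave the patient in the Baseline group and flag or separately tabulate the events that follow.

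Keep the as-randomized set for the 6-month mortality and morbidity noninferiority analyses. Because deaths and renal hospitalizations can appear both as SAEs and as critical events, footnote both sets of tables to say that such an event may be counted under different groupings.

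The data are already collected: 8.7 records vial code, volume, date and time of each administration, and 8.5 covers medications and procedures to Follow-Up 3. The cost is wording, one population flag, and slightly different denominators between the AE tables and the 6-month tables. Reporting the number of undosed and wrong-agent patients by arm would replace the assumed shares used here with observed ones.
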